8.2 PRIMARY ENDPOINT

The primary endpoint will be a comparison of overall survival using time to event (i.e. death) analysis. Time for death will be collected from the quality registries used within oncology for the Swedish study population. For other countries, there will be local procedures to capture this data.

9 STUDY DESIGN

9.1 STUDY OUTLINE

This is a prospective, randomized, open label, multinational, multicentre study.

Date: 28 Oct 2016 15 (31)

^{*} when updating the protocol, it is obvious that the different parts of the study (breast or colorectal) will have different time frames. The breast cancer cohort has higher recruitment rate than the colo- and rectal cancer cohorts. Accordingly, recruitment of breast cancer patients will be completed earlier.

The study will include 8,000 patients. The study will include up to 20 sites in Sweden, Poland, Ireland and China. The population will be patients that are scheduled for radical breast- or colorectal cancer surgery in general anaesthesia. The patients included in the study will be randomized to either propofol anaesthesia or sevoflurane anaesthesia.

In connection with the preoperative anaesthetic procedures (according to local procedures) the patient will be screened and consented for the study. Demographic data will be collected in connection with screening/enrolment. Once enrolled, the patient will be randomized to either propofol anaesthesia or sevoflurane anaesthesia. The anaesthesia is then performed according to standard institutional procedures at each site. Anaesthesia related and surgical related variables during the surgery and during the postoperative course (until 30 days after surgery) will then be collected. Data about survival and other tumour specific data will be transferred from the quality registries used within oncology for the Swedish study population. For other countries, there will be local procedures to capture this data.

The only study specific procedure for this protocol is the randomisation. Data will then be collected from the Medical Records generated during the patient's normal care (demographics, anaesthesia- and surgical related data). Tumour-specific and survival data will be transferred via the quality registries used within oncology for patients enrolled in Sweden respectively. For other countries, there will be local procedures to capture this data.

9.2 SCHEDULE OF EVENTS

A summary of study events to be performed each treatment period is presented in the tabular format in Appendix 1.

10 SELECTION AND WITHDRAWAL OF PATIENTS

10.1 SUBJECT INCLUSION CRITERIA

- 1. Be informed of the nature of the study and have provided written informed consent
- 2. At least 18 years of age
- 3. Patient that is scheduled for elective radical breast- or colorectal cancer surgery in general anaesthesia. Radical surgery means that the aim of the surgery is to cure (adjuvant treatment such as chemotherapy and/or radiation therapy seen as part of the curative treatment).

10.2 SUBJECT EXCLUSION CRITERIA

- 1. The surgery that is going to be made is an acute surgical procedure
- 2. The surgery that is going to be made is palliative surgery

Date: 28 Oct 2016 16 (31)

- 3. Known or suspected hypersensitivity to either propofol or sevoflurane or presence of any contraindication according to the substances' valid SPC.
- 4. Lack of suitability for participation in the trial, for any reason, as judged by the Investigator (e.g. communicative disturbances (language or intellectual))

10.3 WITHDRAWAL OF SUBJECTS

As noted in section 17.4, the subjects will be notified of their voluntary participation and of their freedom to withdraw from study. As there are no study specific procedures other than randomization in this study, a withdrawal of a subject will result in that no more data capture in the CRF will be made.

10.4 SUBJECT LOG AND SCREENING OF SUBJECTS

Each study site will recruit patients from their own patient flow.

It is the responsibility of the Investigator at each site that all patients, considered as candidates for the study, are listed in the "Screening and Enrolment log".

Patients will receive a consecutive screening number when signing the informed consent and are thereafter considered to be study patients. Once they have been randomized, they will also get a patient-specific randomization number and they are considered as enrolled in the study.

It is the responsibility of the investigator to keep a patient identification list, identifying each individual study patient.

11 TREATMENT OF SUBJECTS

11.1 TREATMENT ADMINISTRATION

The patient will be randomized to either propofol or sevoflurane anaesthesia. Both these anaesthetics are well established within clinical practice since many years. All sites / Principal Investigators participating in the study have long experience from both inhalational- and propofol based anaesthesia.

The products will be used according to currently available SPC (Summary of Product Characteristics) and according to normal clinical practice at each participating site.

11.2 DESCRIPTION OF INVESTIGATIONAL PRODUCTS

Propofol registered products with propofol that are available on the

markets in the participating countries, e.g. Diprivan®,

Propofol-Lipuro[®], and Propolipid.

Sevoflurane registered products with sevoflurane that are available on the

markets in the participating countries, e.g. Sevofluran Baxter

and Sevorane®.

Clinical Study Protocol CAN version FINAL 2.0

Date: 28 Oct 2016 17 (31)

The protocol allocates which treatment arm that will be used for each patient but not which specific hypnotic product within each treatment arm that will be used. Each participating site can decide this and will use the hypnotic product they have within their normal clinical routines.

More detailed information about the products is available in the SPC of each product.

11.3 PACKAGING AND LABELLING OF INVESTIGATIONAL PRODUCTS

The hypnotic products used in this study will not be provided by the Sponsor (academic Sponsor). The distribution of the products will be made through each site's normal distribution system.

The hypnotic products will not be labelled according to procedures in connection with clinical trials. The products are used according to normal clinical procedures and the study is observational.

11.4 STORAGE AND HANDLING

The products will be stored according to storage conditions noted in the SPC of each product.

11.5 RANDOMISATION AND BLINDING

The study patients will be randomly allocated to either propofol- or sevoflurane-group in a 1:1 ratio. The randomisation list is generated by computer in a permuted block fashion and transferred to a sequence of sealed, opaque, consecutively numbered envelopes. When a patient is considered eligible for the study and has given informed consent, randomisation is performed by opening the next envelope in sequence. Once assigned a treatment group by randomisation, a subject cannot be "unrandomised" or "de-registered" from the study population. Moreover, "cross-over" between treatment assignments (i.e. propofol to sevoflurane, or vice versa) will not be permitted.

Blinding is not applicable – open label study.

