14 STATISTICS AND DATA MANAGEMENT

14.1 DATA MANAGEMENT

UCR will be responsible for the Data Management of the clinical database and will write a study specific Data Management Plan (DMP) where further details will be specified.

An electronic CRF will be used in this study which also will serve as the clinical database for the study. UCR will be responsible for set-up, support and management of this electronic CRF. All demographic, anaesthesia related and surgical related data will be collected in this database.

This system will also include handling of queries to resolve any inconsistencies detected by the quality control procedures.

Tumor-specific variables including data about survival will not be part of this database but will be transferred from the quality registries used within oncology for the Swedish study population. These quality registries are routinely used within oncology as part of the quality assurance of the care of these patients (the INCA-platform is used). The registries are handled by six Regional Cancer Centers (RCC). The RCC registers includes a quality register for breast cancer, which was started in 1992 but also registers for colon cancer and rectal cancer which was started in 1995 and in 1997 respectively. These registers contain information on mode of detection, histopathology, and stage of cancer at diagnosis, other prognostic markers and complementary treatment given. Hence, complete oncologic- and outcome data will be available for all types of cancer included in the study within the defined period of time. Data on type and stage of the cancer, as well as different prognostic markers recorded in the oncologic registers will be extracted, as well as data on recurrences of disease, vital status and date and cause of death.

In order to be able to link the information in these databases, the patient's full personal identification number will be collected and noted for the Swedish and Polish study population. No personal identification number will be captured for the patients enrolled at the sites in other participating countries. The personal identification number will be deleted after data cleaning and merge of the databases, to ensure anonymity for each person. All analysis made will be on the whole population when the personal identification has been removed.

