16 QUALITY CONTROL AND QUALITY ASSURANCE

16.1 SOURCE DATA

Generally, the Medical Records / laboratory reports / anaesthetic reports will serve as source data. CRF can also be used as source data.

Following general Definition of Source Data location will apply for all sites and thus is no site-specific document made:

- The randomization sheet which is included in the randomization envelope is the source for randomization data. This sheet is filed in Investigators File.
- Date of signed Informed Consent is noted on the originally signed document. This serve as source for data of consent-data.
- Medical Notes is seen as source data for all other variables.

A site-specific Origin of Source Data-log needs to be compiled at the site if there are changes to these general Source Data location procedures.

Clinical Study Protocol CAN version FINAL 2.0

Date: 28 Oct 2016 23 (31)

The following minimum amount of information should be recorded in the hospital records:

- Clinical study number.
- Subject identification.
- Date when patient information was given and when signed Informed Consent was obtained.
- Diagnosis.
- Fulfillment of eligibility criteria.

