16.2 MONITORING

In accordance with the principles of Good Clinical Practice (GCP), monitoring of the study will be arranged by the Sponsor. UCR has been appointed by the Sponsor to monitor this study for the Swedish sites and for the central monitoring of the database - see below. For other participating countries, the Sponsor will appoint local monitoring organisation to perform on-site monitoring activities and regular contacts. During the study, the Monitor will have regular contacts with the study site(s), including visits to ensure that the study is conducted and documented properly in compliance with the protocol, GCP and applicable regulatory requirements.

Both centralized monitoring activities and on-site monitoring activities will be used in this project. It has been decided that the major part of the monitoring will be made by centralized methods together with regulary telephone contacts with site but with limited on-site activities. This decision is based on the nature of the study – observational with no other study specific procedures than the randomization. Additionally, the investigational products used are well established within clinical practice since many years and with documented safety profile.

Each site will have a site initiation (can be organised as multi-centre initiation meeting or web-based training) with focus on providing information about study objectives, study procedures and CRF-training. Each site will then have at least one on-site visit during the study. Based on the outcome of centralized monitoring activities, the frequency of on-site monitoring activities may be increased. The Monitor will review source documents for verification of consistency with the data recorded in the eCRFs for a random sample of patients. The Monitor will also provide information and support to the Investigator(s).

The centralized monitoring will be used to detect each site's level of compliance in terms of completion of CRF generally but also with focus on critical data (e.g. compliance in randomization to propofol or sevoflurane and date of surgery). The outcome of the statistical checks that will be used will indicate whether increased monitoring activities are needed on a specific site.

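### Open-label permuted-block envelopes combined with an any-reason exclusion leave room for selection before allocation; a stated control on predictability would be a cheap improvement

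*Protocol*

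**What the plan says.** Section 11.5 fixes the allocation method with equal numbers planned for the two arms. On how assignments are produced and delivered: "The randomisation list is generated by computer in a permuted block fashion and transferred to a sequence of sealed, opaque, consecutively numbered envelopes". On timing: "When a patient is considered eligible for the study and has given informed consent, randomisation is performed by opening the next envelope in sequence". The same section bars removing a patient once assigned, bars switching between arms, and ends: "Blinding is not applicable – open label study".

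Exclusion criterion 4 in Section 10.2, repeated in the synopsis, reads: "Lack of suitability for participation in the trial, for any reason, as judged by the Investigator". The example it gives is a communication difficulty.

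On records, Section 16.1 states: "The randomization sheet which is included in the randomization envelope is the source for randomization data". That sheet goes into the investigator's file. Section 13.1 also makes the allocation and the hypnotic actually used recorded variables, and Section 10.4 gives each randomised patient a number and requires a log of all candidates.

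On oversight, Section 16.2 says that "the major part of the monitoring will be made by centralized methods", with at least one visit per site. It gives adherence to the allocated arm and the surgery date as examples of critical data. Section 14.1 adds: "An electronic CRF will be used in this study which also will serve as the clinical database for the study".

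**The concern.** Opaque envelopes hide the next assignment itself, but not what earlier assignments in the same block imply about it. In an open-label trial the team that opens envelopes also sees what was assigned before. If the end of a block can be worked out, a discretionary exclusion gives an unchallenged way to leave out a patient, or to postpone one until the next envelope suits.

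The stake is the comparability of the arms at entry. Death is an objective endpoint, but that gives no protection against unequal arms at baseline, and analysing patients by randomised arm does not undo it. Staff may also hold expectations: Section 6 sets out reasons why inhalational agents might worsen survival after cancer surgery. Section 9.1 names randomisation as the one procedure that the study adds to usual care, so the causal comparison rests on it.

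**Working it through.** The protocol gives no figure for predictability, so there is none to reproduce. The sample size in Section 14.3 is not in question; its total of 8,000 is used below only for scale.

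**Step 1: what each stated safeguard acts on.**

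| Safeguard | Section | Acts on | Stops refusal or delay before opening? |
|---|---|---|---|
| Sealed, opaque, numbered envelopes | 11.5 | Reading the content early | No, if the arm is inferred from past assignments |
| Eligibility and consent before opening | 11.5 | Reversal after the arm is seen | No, the inference comes earlier |
| No removal, no cross-over | 11.5 | The time after opening | No |
| Log of all candidates | 10.4 | Listing of patients | No; no reason or time of exclusion is required |
| Central checks | 16.2 | Adherence to arm, surgery date | No; these concern patients already randomised |
| Consent log sent to the monitor | 16.2 | The consent process | No; at most it leaves a trace of patients who consented and were not randomised |

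**Step 2: how much could be foreseen.** Inputs: 1:1 allocation, permuted blocks and open label (Section 11.5). Assumptions not in the protocol: block size m is fixed, known to staff, and kept within one sequence whose past assignments they can see.

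With m/2 places per arm, the rest of a block is certain once one arm is used up. The expected number of certain places per block is 2m/(m+2), so the share of all allocations is 2/(m+2).

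Check by hand for m = 4. There are six equally likely orders. AABB and BBAA each give 2 certain places; the other four give 1 each. The total is 2×2 + 4×1 = 8 of 6×4 = 24 places, or 33.3%.

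Full enumeration of all orders gives:

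| m | Certain places per block | Share certain, 2/(m+2) | Of 8,000 | Correct guesses, betting on the arm behind |
|---|---|---|---|---|
| 4 | 1.333 | 2/6 = 33.3% | 2,667 | 70.8% |
| 6 | 1.5 | 2/8 = 25.0% | 2,000 | 68.3% |
| 8 | 1.6 | 2/10 = 20.0% | 1,600 | 66.6% |

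Over a wider range, the certain share is 50.0% at m = 2 and 14.3% at m = 12. Without foresight, half of all guesses are correct. If sizes are varied and withheld, or blocks are not kept within a sequence that staff can observe, the certain share is lower and cannot be computed from the protocol.

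**Step 3: from predictability to bias.** This would need the share of foreseeable places that were exploited, the prognosis of the patients moved, and the direction of steering. The protocol supplies none of these, so the calculation stops here.

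**The case against.** Sealed, opaque, numbered envelopes opened in order after consent are a recognised method, and removal afterwards is barred. Criterion 4 is a usual clause. Leaving block size out of a protocol is common and can itself protect concealment; the detail may sit in a randomisation plan that is not shown. All of this stands. Neither the missing block size nor criterion 4 is an error on its own.

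A reader might infer that the sheet in the envelope is the only trace of the allocation. The documents do not support that. The sheet is the source, but Section 13.1 records the allocation as well, Section 10.4 assigns a randomisation number and Section 18.1 requires a CRF for every randomised patient.

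A reader might also infer that monitors have no means of seeing the order of opening. That goes too far. Consent dates, surgery dates and randomisation numbers could reveal gross departures if the numbers follow envelope order, which is not stated, and the critical data in Section 16.2 are examples rather than a closed list. What remains is that no check of opening time is described, and no stated check targets patients refused or postponed beforehand.

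Motive can also be overstated. Section 6.1.4 reports that significance in the sponsor's retrospective study disappeared after adjustment, and Section 17.3 cautions that animal findings may not hold in humans. Staff who believed sevoflurane harmful might steer frail patients towards propofol, which would work against the hypothesis.

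**Conclusion.** The point holds as a cheap improvement, not as a demonstrated flaw. The protocol combines visible past assignments, permuted blocks, envelopes and discretionary refusal. It describes no control on predictability, custody or the moment of opening, so selection before allocation is neither prevented nor looked for.

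The size is conditional: 20% to 33% of allocations certain in advance for blocks of 8 down to 4, if blocks are fixed, known and within one observed sequence, and fewer otherwise. That envelopes are used at the sites is itself an inference from the filing rule in Section 16.1.

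It would be tempting to conclude that staff can in fact foresee allocations, or to attach a bias in five-year survival to be set against the 5-point target. The document supports neither, because block size is not given and every further input would have to be invented.

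**What to change.** For remaining recruitment, amend Section 11.5 so that the allocation is released through the eCRF only after identity, tumour type and all eligibility answers have been entered and locked, with a reason for any use of criterion 4.

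If the eCRF cannot randomise (the protocol does not say whether it can), or if some sites keep envelopes:
- use randomly varied block sizes, withheld from sites;
- write the screening number, date and time on the sealed envelope before it is opened;
- enter the envelope number and opening time in the eCRF the same day;
- add to Section 16.2 a central check of sequence and timing against the screening and enrolment log.

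Cost: an amendment, one form or log line per patient, and a change of procedure during the trial. Enrolment was planned to start in 2013 (Section 6.2) and this version dates from October 2016, so patients already randomised gain no protection. Treatment, endpoint and sample size are unaffected.

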11.6 CONCOMITANT THERAPY

No protocol-specific restrictions in terms of concomitant therapy. Information about re-anaesthesia / re-surgery (if applicable) within 365 days after surgery will be collected.

11.7 COMPLIANCE WITH THE TREATMENT

Not applicable – the products are prescribed and used according to normal clinical practice at each site.

18 (31)

Date: 28 Oct 2016

11.8 ACCOUNTABILITY OF INVESTIGATIONAL PRODUCTS

No patient specific drug accountability will be documented. The actual hypnotic product given will be noted in the CRF.

12 ASSESSMENT OF EFFICACY

Not applicable – no efficacy variables are used in this study.

13 ASSESSMENT OF SAFETY

13.1 VARIABLES TO BE COLLECTED

Following variables noted during the care of the patient will be recorded – time for data capture of the different variables is noted in the Flow Chart, Appendix 23.1:

Demographic variables including habits and general health

- Age, Gender
- Place of residence, zip code (proxy for socio-economics)
- · Length, Weight
- Smoking (pack years; 1 pack year = 20 cigarettes/day for a year) and Alcohol (standard drinks; 1 standard drink = 12 g pure ethanol)
- ASA-grades
- Co-morbidity
- On-going medication
- Other anaesthetics last year (date, duration, type of)

Study specific variables:

• Randomisation, i.e. allocation to either propofol or sevoflurane-group and confirmation of hypnotic product used during surgery

Anaesthesia related variables

- Duration of current anaesthesia
- Doses of intraoperative opioids during current anaestesia
- Other adjuvant intraoperative treatment such as inotropic drugs
- Accumulated time with mean arterial pressure (MAP) under 65 mmHg or over 130 mmHg
- Accumulated hydration balance at the end of surgery
- Bleeding volume
- Transfusions (red blood cells, plasma)
- Pre-and postoperative laboratory-analyses (see section 13.5 below)
- Complementary regional blockade (which kind of block, type and doses of local anaesthetics)
- •Use of Patent blue V
- Doses of postoperative morphine or other opioids
- Antiemetics and anti-inflammatory drugs
- Re-anaesthesia (type of)

19 (31)

Clinical Study Protocol CAN version FINAL 2.0
Date: 28 Oct 2016

Surgical variables

- Cancer location
- Date of surgery
- Duration of surgery
- Surgical (intraoperative) complications
- Postoperative complications / postoperative morbidity related to surgery
- Re-surgery (date, duration, indication)

Following tumour specific variables are not included in the CRF (will be transferred from the cancer quality registries for the Swedish study population. For other countries, there will be local procedures to capture this data):

- Tumour data (i.e. stage, proliferation, hormone status)
- Complementary therapy (e.g. radiation, chemotherapy, anti-hormone, antibody, angiogenesis inhibitors)
- Recurrence/metastasis (localisation, local/regional/ generalized, time point)
- Re-surgery (date, duration, indication)
- Date of death and cause of death, when applicable

